**9. CCIs at 1 hour and  $\geq 18$  but  $< 30$  hours post-PLT transfusions**

A linear mixed-effect model [3] will be fitted with a single covariate indicating the randomized treatment assignment and a subject-level random effect introduced to model the between-subject heterogeneity and accommodate a within-subject dependence in CCI values. The coefficient of the binary treatment covariate will be estimated and a 95% confidence interval for it will be computed along with a p-value for the test of no effect. These results will be supplemented by an estimate of the group means based on the linear mixed-effect model.

As per the CIP, collection of subject PLT count  $\geq 18$  but  $< 30$  hours post-PLT transfusion episode is not mandatory. As a result, there may be limited amount of data available to fit the model proposed. If the model will not converge due to lack of data, the CCI data will be summarized at the subject level. That is, if the subject has only one transfusion episode, the single CCI value will be used; and for subjects who have multiple transfusion episodes, the average CCI across their transfusions will be used as their subject-specific number. These subject-specific (mean) CCI values will then be used to calculate group mean CCI values for both MIRASOL and CONTROL groups at both one (1) hour (measured between  $\geq 10$  minutes and  $\leq 4$  hours) at 24 hours (measured between  $\geq 18$  and  $< 30$  hours). The mean subject-specific CCI estimate for each treatment group at each of these time points will be presented along with differences in means for the pairwise comparison (MIRASOL vs CONTROL).

## 10. Total number of Red Blood Cell transfusions (number of units)/subject

The analysis of this secondary endpoint, the total number of RBC transfusions (units), will be analyzed using the negative binomial regression model, mirroring the approach outlined for secondary endpoint #6. The only difference being that here, instead of the number of PLT transfusion episodes, the number of RBC transfusion units will be counted for each subject. Consequently, mean rate for the MIRASOL group ( $\lambda_T$ ), and, mean rate for the CONTROL group ( $\lambda_C$ ) will be based on the average number of RBC transfusion units. The offset in the negative binomial model will be the natural log of time in days from Day 0 to date of their last study visit in the treatment period completed. The natural log of the mean rate of the MIRASOL group minus the natural log of the mean rate of the CONTROL group, i.e.  $\ln(\lambda_T) - \ln(\lambda_C)$ , will be used to compare study arms. The corresponding 95% CI and p-value will be displayed such that negative values of difference between  $\ln(\lambda_T)$  and  $\ln(\lambda_C)$  favor the MIRASOL group by reflecting lower utilization.

## 8.3. Exploratory Endpoints

Four Exploratory Endpoints will be considered in this study, and, results of all analyses will be descriptive in nature. Each Exploratory Endpoint, as well as its corresponding analytic approach, is detailed below. All analyses will be based on the mITT population.

### 1. Total number of units of PLTs transfused/day of PLT support

For each subject, the number of units (a PLT unit is defined as one [1] single PLT bag) will be totaled and divided by that subject's number of days of PLT support. Consequently, each subject will have a value for the total number of PLT transfusion units started per day of PLT support. A day of PLT support is defined as any day in which a study PLT transfusion was started. Transfusions lasting more than twenty-four (24) hours will be counted as multiple days of PLT support. These values will then be averaged across subjects and will be displayed for each treatment group (MIRASOL vs CONTROL).

### 2. Total number of PLTs (PLT dose) transfused/Body Surface Area/day of PLT support

For each subject and transfusion episode, the PLT dose, i.e. the number of PLTs in a component (as defined in the denominator of the CCI equation), will be divided by the subject's baseline BSA which is calculated using the following equation:

$$\text{BSA (m}^2\text{)} = 0.007184 \times \text{Height (cm)}^{0.725} \times \text{Weight (kg)}^{0.425}$$

Similar to the analysis of the First Exploratory Endpoint, this value will be divided by the number of days that subject received PLT support. These values will then be averaged across subjects and displayed for each treatment group (MIRASOL vs CONTROL).

### 3. Interval between PLT transfusion episodes (days)

Only subjects with two or more transfusion episodes will be considered in this descriptive analysis. Additionally, if a subject has more than one transfusion episode in a day, this will be counted as a single transfusion episode for the purposes of this analysis. For each subject, the interval(s) between transfusion episodes will be recorded in days. If a subject has two transfusion episodes, the interval between PLT transfusion episodes will begin on the day after the initial transfusion episode ends and will end on the day prior to the start of the subsequent transfusion episode. For instance, if a subject has a transfusion episode on study Day 5, and then another transfusion episode on study Day 6, the interval is zero days. Likewise, if a subject has a transfusion episode on study Day 5, and then another transfusion episode on study Day 7, the interval will be 1 day. If a subject has three transfusion episodes, the two intervals between the three transfusion episodes will be determined using the same process described for a subject with two transfusion episodes, and the average length of the two intervals will then be calculated, i.e. (length of interval 1 + length of interval 2)/2. This average will be used in calculating the overall average. This pattern will be repeated for subjects with four transfusion episodes where the three intervals will be averaged, and so on for individuals with greater numbers of transfusions. The overall average number of days between PLT transfusion episodes will be summarized by averaging these subject-specific averages overall and for each treatment type (strata) by treatment group (MIRASOL vs CONTROL).

#### **4. Platelet refractoriness defined as 2 sequential transfusion episodes, each with CCIs < 7500 measured 1 hour post-transfusion**

This analysis will mirror the analysis performed on Secondary Endpoint # 4. The only difference being, PLT refractoriness is defined as 2 sequential transfusion episodes each with CCIs < 7500 measured 1-hour post-transfusion.

### **8.4. Safety Endpoints**

All Safety Endpoints will be analyzed using the SS. Safety will be evaluated by assessment of physical examinations, vital signs, clinical laboratory values, and TEAEs.

#### **8.4.1. Physical Examinations**

Physical examinations are conducted at baseline and will be listed along with Medical and Surgical History. Results from physical examinations conducted through the course of bleeding assessments are reported as a part of the bleeding outcome.

#### **8.4.2. Vital signs**

Available data on vital signs (e.g., temperature [F°]), heart rate [HR] [beats/min], respiratory rate [breaths/min], systolic blood pressure (BP) (mmHg), diastolic BP [mmHg], SpO2 [%], and position [sitting, standing, supine]) will be reported utilizing appropriate thresholds by age group for each of the pre-, during, post- timeframes for each subject's transfusion. Data will be listed by treatment group and subject. See the CIP for information on the collection of vital signs.

#### **8.4.3. Clinical Laboratory Values**

All laboratory values will be reported in International System of Units.

Hematology is collected at baseline, Day 0 and daily when hospitalized and for clinical visits days. Hematology results include white blood cells ( $10^3/\mu\text{L}$ ), RBCs ( $10^6/\mu\text{L}$ ), hemoglobin (g/dL), hematocrit (%), and platelets ( $10^3/\mu\text{L}$ ), and will be summarized by study day. Hematology data will be listed by treatment group and subject. Neutrophils and lymphocytes will only be included in the listing.

Coagulation laboratory tests (prothrombin time (seconds), International Normalized Ratio (INR), Activated Partial Thromboplastin time (aPTT) (seconds), and fibrinogen (mg/L)) are collected at baseline

and, if available, as part of routine care in follow-up. These labs will be summarized by study day. Coagulation laboratory tests will be listed by treatment group and subject.

Screening and Post-transfusion period Follow-up/Early Termination Cytomegalovirus (CMV) testing will be performed using an Immunoglobulin G (IgG) test. The results will be listed and summarized by study day.

#### **8.4.4. Treatment Emergent Adverse Events**

The following will be displayed.

- Overall TEAEs
- Platelet Transfusion Related TEAEs
- Medical Device Related TEAEs
- TEAEs by maximum severity
- SAEs
- UADEs
- Pulmonary events
  - Subjects on assisted ventilation
- TEAEs causing discontinuation from the study
- All-cause mortality
- Death due to bleeding as the primary or contributory cause of mortality

All TEAEs/SAEs identified during the reporting period (i.e. from initial post randomization platelet transfusion through seventy-two (72) hours following the transfusion end time of the last on-protocol PLT transfusion; for deaths including deaths due to bleeding through thirty (30) days following the transfusion end time of the last on-protocol PLT transfusion) will be followed until resolution, stabilization, or the end of subject's study participation, whichever is first.

Treatment Emergent Adverse Events are defined as those that occur during or following the first post-randomization PLT transfusion. The AE start date and time and transfusion start date and time of the first study transfusion will be used to identify TEAEs. The transfusion end time of the subject's final study transfusion will be used to identify the end of the 72-hour reporting period (or 30 days for deaths). AEs with missing/impartial start date and or time will be considered to be treatment emergent.

Treatment Emergent Serious Adverse Events (TESAEs) are defined as TEAEs marked serious by the investigator. Transfusion-related TEAEs are described through the reporting of TEAEs identified as related to the study treatment or those related to the medical device.

Unanticipated Adverse Device Effects are any serious adverse effect on health or safety or any life threatening problem or death caused by, or associated with, a device, if that effect, problem, or death was not previously identified in nature, severity, or degree of incidence in the investigational plan or application, or any other unanticipated serious problem associated with a device that relates to the rights, safety, or welfare of subjects

Unanticipated Adverse Device Effects will be identified as treatment emergent adverse events reported by the investigator as serious, unanticipated, at least possibly related to study device or at least possibly related to study treatment.

Medical Dictionary for Regulatory Activities preferred terms in the associated SOC and Standard Medical Queries (SMQs) will be used to categorize TEAEs of “Pulmonary events” and additionally those pulmonary events requiring assisted ventilation as defined by the investigator.

Subject related TEAE counts will be summarized using frequencies and percentages. A subject will only be counted once per category of summarization (i.e. if a subject has multiple TEAEs, the subject will only be counted once in the overall ‘Any TEAE’ row but will be counted in each row for specific TEAEs). Event counts will be summarized using frequencies of events by treatment group.

A summary of TEAEs will be generated summarizing the number of TEAEs, TESAEs, unanticipated TESAEs, and UADEs. The number and percent of subjects with at least one TEAE, TESA, TEAE related to study treatment, TEAE related to medical device(s), and TEAEs of pulmonary events and additionally those requiring assisted ventilation will also be included. The number of TEAEs by severity, relationship to study treatment (platelet transfusion) and relationship to the medical device, will be included.

Summary tables by SOC and PT will be reported for TEAEs, TESAEs, unanticipated TESAEs, UADEs, and Pulmonary related TEAEs as well as those pulmonary events requiring assisted ventilation. The number and percent of subjects with at least one event will be presented overall and, at most, once per SOC and PT.

All TEAEs will be listed by treatment group and subject. There will be a separate listing of TESAEs by treatment group and subject.

The timeframe for reporting death as part of AEs and death as a safety endpoint are different. The timeframe for reporting death as an AE is from randomization through thirty (30) days following the last per protocol PLT transfusion, where the timeframe for reporting death as a safety endpoint of death is through Day 56. The number of deaths through thirty (30) days following the last on-protocol PLT transfusion will be summarized by relationship to study treatment (PLT transfusion) and by relationship to medical device(s). The total number of deaths through Day 56 will be reported.

All deaths will be listed by treatment group and subject. This listing will include the investigator assessment of cause of death.

Deaths due to bleeding will be defined by the applicable bleeding grade and reported in the clinical study report. No listings or summaries will be produced as part of this reporting effort.

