### **6.1. Study Design**

This is a prospective, multi-center, controlled, randomized study in which a non-inferiority (NI) design will be employed to evaluate the clinical effectiveness of Mirasol (MIR)-treated versus Conventional (CONTROL) apheresis (Aph) platelets (PLTs) in subjects with hematologic malignancies with hypoproliferative thrombocytopenia expected to have PLT count(s)  $\leq 10,000/\mu\text{L}$  and requiring  $\geq 2$  PLT transfusions. Subjects will be randomized by a ratio of 1:1 (MIRASOL vs CONTROL group) using a permuted-block schedule stratified by investigational site and type of treatment (allogeneic transplant vs autologous transplant vs chemotherapy). Randomization will occur as close to the initiation of the first study transfusion as possible, within five (5) days prior to the anticipated initiation of PLT transfusion(s).

Subject participation will be for up to eighty-one 81 days; a 14-day screening period, a 28-day treatment period, and a 28-day follow-up period. Study Day (also referred to in this document as ‘Day’) 0 of the treatment period is defined as the day of the first study transfusion following randomization. The primary, secondary, and exploratory endpoints will be based on data captured during the treatment period (Day 0 to transfusion independence or Day 28, whichever comes first). Transfusion independence is defined as ten (10) days without a PLT transfusion prior to date of last contact or Day 28 whichever is earlier. The date of transfusion independence will be the 10th day without a PLT transfusion.

Daily bleeding assessments assess bleeding for the previous day. The first bleeding assessment to be used for analysis of primary and secondary endpoints etc., will be collected on Study Day 1 which assesses bleeding at Study Day 0. Bleeding assessments are planned to occur on Study Days 0-27 and at the post transfusion follow-up visit. Consequently, there will be a maximum of 28 bleeding assessment days used for analysis. The bleeding assessments to be included in analysis are greyed out the in schematic below.

Study Day	0 (first transfusion day)*	1	2	3	4	5	6	27	Post transfusion/ Follow-up (in some cases Study Day 28)
Day bleeding assessed (24 hours previous to Study Day)	-1	0	1	2	3	4	5	26	27 + 2-day window allowed for visit

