### **7.5.2. Modified Intent-to-Treat Analysis Set**

The mITT analysis set is defined as containing all randomized subjects who undergo at least one (1) study transfusion post-randomization based on the treatment group to which they were randomized. Subjects will be analyzed according to the treatment group (MIRASOL or CONTROL) they were assigned at randomization.

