## 7.7. Calculation of Study Day and Treatment Period

The day the subject receives their first post-randomization PLT transfusion will be considered Day 0. If the subject's PLT transfusion episode spans two calendar days, the day the transfusion started will be considered Day 0.

The treatment period is defined as the period of time from Day 0 through Day 27 or to the day of transfusion independence, defined as the last of ten (10) successive days after the last PLT transfusion (on- or off-protocol), whichever occurs first. Bleeding assessments are conducted at baseline and are to be conducted every day from Day 0 until the post-transfusion follow-up visit or early termination visit.

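### Section 8.4.4 ends the same safety reporting period at two different transfusions, so TEAE counts are not determined for subjects who finish on off-protocol platelets

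*SAP*

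**What the plan says.** SAP section 8.4.4 first describes a reporting period that runs from the first post-randomization platelet transfusion "through seventy-two (72) hours following the transfusion end time of the last on-protocol PLT transfusion", and for deaths "through thirty (30) days following the transfusion end time of the last on-protocol PLT transfusion". The next paragraph, which explains how TEAEs are identified, gives a different end: "The transfusion end time of the subject's final study transfusion will be used to identify the end of the 72-hour reporting period", with 30 days in place of 72 hours for deaths.

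Later in the section, the period for death as an adverse event is given as "from randomization through thirty (30) days following the last per protocol PLT transfusion". The summary of deaths by relationship to treatment and device again uses the last on-protocol transfusion. Mortality as a safety endpoint is separate: "the timeframe for reporting death as a safety endpoint of death is through Day 56".

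The document supplied as the protocol repeats the same text in its own section 8.4.4. The CIP itself is not among the documents.

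**The concern.** One reporting period has two ends. They coincide when a subject's last platelet transfusion is of the randomized product. They differ when the last transfusion is off-protocol, which the plan expects: section 8.1.1 has rules for exactly these subjects.

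Two programmers could each follow section 8.4.4 and build different TEAE datasets. The choice reaches every TEAE table, because TEAEs are shown as counts and percentages of subjects with no adjustment for time at risk. An event after a final off-protocol transfusion is either in or out, depending on which sentence is followed.

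The Safety Set adds a second difficulty. Section 7.5.3 admits anyone with at least one post-randomization platelet transfusion and groups subjects by the majority product received. Section 7.14 defines on-protocol by the randomized arm. A subject randomized to MIRASOL who received mostly conventional units is tabulated under CONTROL, yet under the on-protocol rule the window closes 72 hours after the last MIRASOL unit. Events that occur on the tabulated product are then discarded.

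**Working it through.** **1. Can the two ends be read as one?** Only if *study transfusion* means on-protocol transfusion. The SAP does not define the term.

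- Section 6.1: Day 0 "is defined as the day of the first study transfusion following randomization".
- Section 7.7: "The day the subject receives their first post-randomization PLT transfusion will be considered Day 0".
- Section 7.5.2, mITT: subjects who "undergo at least one (1) study transfusion post-randomization based on the treatment group to which they were randomized".

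The first two describe the same day, so *study transfusion* appears to mean any post-randomization platelet transfusion. The third could support a narrower meaning. The balance is against reading the two ends as the same.

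**2. Difference per subject.** Let *a* be the day of the last on-protocol transfusion and *b* the day of the last platelet transfusion of any kind. Clock times are ignored. The on-protocol rule ends at *a* + 3 (deaths *a* + 30) and the other rule at *b* + 3 (deaths *b* + 30). The days lost are *b* − *a*. Section 7.13 allows transfusions from Day 0 to Day 27, so the range is 0 to 27.

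| a | b | AE window ends, two rules | Death window ends, two rules | Days lost |
|---|---|---|---|---|
| 14 | 14 | 17 / 17 | 44 / 44 | 0 |
| 14 | 21 | 17 / 24 | 44 / 51 | 7 |
| 0 | 27 | 3 / 30 | 30 / 57 | 27 |

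A subject with no on-protocol unit has no *a*, so the on-protocol rule gives no window end.

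**3. Observed time by randomized arm.** The documents give no off-protocol rate, so all inputs here are assumptions: 279 per arm (558/2), mean full window *W* = 18 days, and mean loss *L* = 7 days among subjects who end off-protocol. Days lost per arm are 279 × *s* × *L*, where *s* is the share ending off-protocol. The MIRASOL/CONTROL ratio of observed days is (*W* − *s*M·*L*)/(*W* − *s*C·*L*).

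- 5% in each arm: 98 versus 98 days lost, ratio 1.000.
- 15% MIRASOL, 1% CONTROL: 293 versus 20, ratio (18 − 1.05)/(18 − 0.07) = 0.945.
- 30% MIRASOL, 2% CONTROL: 586 versus 39, ratio (18 − 2.1)/(18 − 0.14) = 0.890.

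With *W* from 12 to 24 and *L* from 3 to 14 (*L* < *W*), the unequal-rate cases tried give ratios from 0.994 (5% versus none, *W* = 24, *L* = 3) to 0.779 (30% versus 2%, *W* = 18, *L* = 14).

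**4. Percent with any TEAE in the displayed columns.** Assume a constant hazard of 0.05 per day in both groups, transfusions to Day 20 (window 23 days), 20% of the MIRASOL-randomized subjects switching for good, and no switching in CONTROL.

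- Full window: 1 − exp(−0.05 × 23) = 0.683.
- *Last MIRASOL unit on Day 14, subject stays in the MIRASOL column.* Window 17 days: 1 − exp(−0.05 × 17) = 0.573. MIRASOL column: 0.8 × 0.683 + 0.2 × 0.573 = 0.661. Result: about 66% versus 68%.
- *Last MIRASOL unit on Day 3, subject mostly on conventional units and so tabulated under CONTROL.* Window 6 days: 1 − exp(−0.05 × 6) = 0.259. About 56 subjects move (0.20 × 279). CONTROL column: (279 × 0.683 + 56 × 0.259)/335 = 0.612. Result: about 68% MIRASOL versus 61% CONTROL.

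There is no true difference in either case, and the sign changes between them.

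**The case against.** The strongest reply is that the on-protocol sentence mainly says which events will be followed to resolution, while the sentence that says how the end of the period is identified names the final study transfusion. If *study transfusion* includes off-protocol units, the analysis rule already covers them and every Safety Set subject has a window. This may well be what was intended. It does not settle the matter: the first sentence states the limits of the reporting period outright, the 30-day death summary later in the section uses the on-protocol anchor again, and the deciding term is undefined.

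Three limits on the concern also stand. A subject who switches and returns to the randomized product loses nothing. Total deaths through Day 56 and the listing of all deaths depend on neither anchor. What was actually collected after a switch depends on the CIP.

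A reader might infer that the on-protocol rule shortens follow-up mainly for MIRASOL and so makes it look safer. Section 7.12 gives some support: *Control Allowed* product is compliant for a MIRASOL subject, whereas any Mirasol product is non-compliant for a CONTROL subject. That makes loss in subjects randomized to MIRASOL probably more frequent. But the on- and off-protocol definitions in section 7.14 mirror each other, no rate is given for either arm, and the tables are not by randomized arm. Leaving the Day 3 switchers in the MIRASOL column would give 0.8 × 0.683 + 0.2 × 0.259 = 0.599, or 60% versus 68%. Under the majority rule they would probably appear under CONTROL, which reverses the sign.

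**Conclusion.** The contradiction stands and should be resolved before the TEAE datasets are built. Under the on-protocol anchor, a subject whose last transfusion is off-protocol loses the days between the last on-protocol and the last transfusion, 0 to 27 days. A Safety Set subject with no on-protocol unit has no window end. The 30-day death summary by relationship is exposed to the same problem.

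The documents do not support a stated bias in favor of MIRASOL. The effect on the displayed percentages depends on the off-protocol rate, the timing of switches and the majority-product grouping. The results of about 66% versus 68% and about 68% versus 61% are illustrations on an assumed hazard of 0.05 per day and 20% switching, not estimates. The primary endpoint is not involved.

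**What to change.** - Define *study transfusion* in the SAP.
- Use one analysis anchor in both groups for the 72-hour and 30-day windows. The end of the last post-randomization platelet transfusion of any type matches the Safety Set definition and leaves no subject without a window.
- Make every sentence of section 8.4.4 that states a window, including those on deaths, use that anchor, and reconcile them with the CIP.
- If adverse-event collection in fact stopped earlier for some subjects, add adverse-event rates per subject-day at risk, so that unequal observation is visible.

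The cost is SAP wording and possibly one extra table.

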- All tables will clearly indicate the sample sizes contributing to the summary data in the column heading and labeled as “*Treatment* (N=)”. For example, if a table reports data for the Full Analysis Set (FAS) population, N would represent all subjects in the FAS. If a table reports data for the Safety Set (SS), N would represent all subjects in the SS. Within the table the small “n” will represent the number of subjects within the population of interest who have non-missing data or data otherwise available for the summary measures of interest (i.e. the denominator for a subset of the overall population being presented in the summary). If no data are available for a TFL, the output will be produced with “No data to display”. Footnotes which are data driven may be applied to the TFLs as needed. These changes will not necessarily be made to the mock TFLs.
- Percentages are calculated out of the header N unless otherwise footnoted.
- Duration of periods of time will be calculated in days as (stop date – start date + 1) in order to include both the starting day and final day of the periods of time. Conversions to weeks, months, or years will be calculated as days/7, days/30.4375, or days/365.25, respectively.
- In general, missing values will be handled as follows: for continuous variables at baseline, missing values will be excluded from calculation of summary statistics and the n of subjects reporting will be reported. For categorical values at baseline, the number and percent of subjects with missing values will be displayed. Handling of missing postbaseline values will depend on the analysis.

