**7. Days of PLT support; the number of days from the first to the last PLT transfusion**

The number of days from the first to the last PLT transfusion will be analyzed using a Cox regression model with the treatment group serving as the lone covariate. Subjects will be censored at Day 27 or on their last study visit in the treatment period. Reported results will consist of the hazard ratio along with the corresponding 95% CI and p-value. A hazard ratio greater than 1 will favor the MIRASOL group because it will correspond to a shorter duration of platelet support. A KM plot contrasting the two study arms will also be generated to provide a visual representation of survival probability as a function of study duration.

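### The non-fatal adverse event window follows each subject's transfusion course, so crude counts and percentages can differ between arms, in either direction, at equal daily risk

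*SAP*

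**What the plan says.** **Start of the window.** SAP 8.4.4: "Treatment Emergent Adverse Events are defined as those that occur during or following the first post-randomization PLT transfusion". That definition has no end point.

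**End of the window.** SAP 8.4.4 gives two. The reporting period for TEAEs and SAEs runs "through seventy-two (72) hours following the transfusion end time of the last on-protocol PLT transfusion". In the next paragraph, the end time of the subject's "final study transfusion will be used to identify the end of the 72-hour reporting period", with no on-protocol condition.

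**Summary measures.** SAP 8.4.4: "Subject related TEAE counts will be summarized using frequencies and percentages", and "Event counts will be summarized using frequencies of events by treatment group". SAP 7.4 fixes the denominator: "Percentages are calculated out of the header N unless otherwise footnoted". No subject-day rate, time-to-event summary or common window is planned for non-fatal events.

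**Related rules.**
- SAP 7.13 allows study transfusions on any day from Day 0 to Day 27.
- SAP 8.2.2, endpoint 7, compares the arms on days of platelet support, "the number of days from the first to the last PLT transfusion", without restriction to on-protocol units.
- SAP 7.14 classes 'Control Allowed' units as off-protocol for a subject randomized to MIRASOL. SAP 7.12 does not class them as non-compliant for that subject.
- SAP 7.5.3 admits a subject to the Safety Set on any post-randomization platelet transfusion and groups by the majority product received.
- For mortality, the "timeframe for reporting death as a safety endpoint of death is through Day 56".

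**The concern.** The time during which a non-fatal event can be counted is not the same for every subject. It depends on when the subject's last qualifying transfusion falls, and that is determined after randomization and may be influenced by the assigned product. A percentage over all subjects, or a raw count, then mixes two things: how often events occur per day, and for how many days anyone was counting.

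The tables affected are those for TEAEs, TESAEs, pulmonary events, and transfusion- and device-related TEAEs. A difference between arms could reflect a product hazard or only a longer window. A real excess could also be hidden by a window that closes sooner.

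Elsewhere the plan allows for unequal observation. The primary analysis (8.1.1) and secondary endpoints 6 and 10 (8.2.2) use a log-time offset, and the mortality endpoint has a fixed end day. Non-fatal adverse events have neither.

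**Working it through.** The documents give no adverse event rates and no expected duration of platelet support, so there is no plan figure to reproduce. The durations and hazards below are assumptions. They show the direction and scale of the effect and do not predict it.

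**1. Range of the window.** Window W = day of the last qualifying transfusion + 3 days (72 hours). A last qualifying transfusion on Day 0 gives 0 + 3 = about 3 days. One on Day 27 gives 27 + 3 = about 30 days.

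**2. Longer on-protocol support.** Assume the same constant daily hazard in both arms.
- Expected count ratio = W(MIRASOL) / W(CONTROL).
- CONTROL support of 10 days gives a window of 13 days.
- MIRASOL support of 11, 12 or 14 days, all on-protocol, gives 14/13 = 1.08, 15/13 = 1.15 or 17/13 = 1.31.
- Percentage with an event = 1 − exp(−h × W). At h = 0.01 per day this is 12.2% in CONTROL against 13.1%, 13.9% or 15.6%.

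Count ratios for other assumed CONTROL durations:

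| CONTROL support | +1 day | +2 days | +4 days |
|---|---|---|---|
| 7 days | 1.10 | 1.20 | 1.40 |
| 10 days | 1.08 | 1.15 | 1.31 |
| 14 days | 1.06 | 1.12 | 1.24 |

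**3. Earlier last on-protocol unit.** Take the sentence that ends the window at the last on-protocol transfusion. Suppose MIRASOL subjects need platelets for 12 days against 10 in CONTROL, but their later units are conventional and so off-protocol. The hazard is chosen so that CONTROL shows 20%.

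| Last on-protocol MIRASOL unit | Count ratio | MIRASOL percentage |
|---|---|---|
| Day 12 | 15/13 = 1.15 | 22.7% |
| Day 10 | 13/13 = 1.00 | 20.0% |
| Day 8 | 11/13 = 0.85 | 17.2% |
| Day 6 | 9/13 = 0.69 | 14.3% |

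The arm that needs platelets for longer then shows the same number of events or fewer. This assumes the subjects stay in the MIRASOL column. Under the majority rule in 7.5.3, a subject who received mostly conventional units would be tabulated under CONTROL and would take the short window there.

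**4. A subject with no defined window.** The Safety Set does not require an on-protocol transfusion. For a subject who has none, the on-protocol sentence gives no end of window. The final-study-transfusion sentence gives one only if that term covers off-protocol units.

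**5. Effect of a subject-day denominator.** With n subjects and constant hazard h, expected events are n × h × W and subject-days are n × W, so the rate is h in each arm and the ratio is 1.00, whichever arm has the longer window. For first events, expected time at risk per subject, stopped at the first event, is (1 − exp(−h × W)) / h. Dividing the expected proportion, 1 − exp(−h × W), by it again gives h.

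**The case against.** **The sign is unknown.** A reader might infer that the arm needing platelets for longer must show more events, or that the window always equals platelet support plus three days. The documents do not support either reading. The reporting-period sentence ends at the last on-protocol unit, while endpoint 7 counts to the last platelet transfusion of any kind. Step 3 shows the ratio falling to 1.00 or below. Nor does the plan say that it expects support to differ by arm; it only specifies a comparison. This part of the objection stands.

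**Much is already covered.** All-cause mortality as a safety endpoint runs to a fixed Day 56, so it is untouched; death reported as an adverse event, to 30 days after the last on-protocol transfusion, keeps a variable window. Bleeding days are analysed as a rate. SAP 7.14 reports the duration of the transfusion period on the Safety Set, so a reader can see whether exposure differs. That helps, but a median, minimum and maximum do not give total subject-days, so the reader cannot rebuild a rate.

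**A rate is not a clean cure.** The window is set by the clinical course after randomization, and dividing by its length does not remove that. The ratio returns to 1.00 only under constant hazard. If events arise from each transfusion, extra events from extra transfusions are a real consequence of the assigned product, and a per-day rate can dilute them. This stands, and it is why the rate should sit beside the percentage and not replace it.

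**No formal test is at stake.** Safety summaries are descriptive. This also stands and limits how serious the point is.

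**Conclusion.** The point holds as a cheap improvement. The window for non-fatal adverse events depends on each subject's transfusion course, and the planned tables have no denominator for time under observation. Crude totals can therefore differ between arms with no difference in daily risk. With one to four extra days of on-protocol support on an assumed 7 to 14 days, counts rise by 6% to 40%. With an assumed earlier last on-protocol unit, at day 8 or 6 against day 10, they fall by 15% or 31%. These sizes rest wholly on assumed durations and equal constant hazards; the documents do not allow the actual size or direction to be derived.

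Separately from any assumption, 8.4.4 gives two ends for the same window, and one of them leaves some Safety Set subjects without an end. That must be settled before any subject-day denominator can be programmed. The primary conclusion, its error rate and the Day 56 mortality endpoint are not affected.

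**What to change.** 1. In SAP 8.4.4, reconcile the two sentences on the end of the reporting window, carry the result into the TEAE definition, and state the window end for a Safety Set subject with no on-protocol transfusion.
2. Keep all planned counts and percentages. For TEAEs, TESAEs, pulmonary events, and transfusion- and device-related TEAEs, add:
   - events per 100 subject-days of the reconciled window;
   - first events per 100 subject-days, with time stopped at the first event;
   - the MIRASOL:CONTROL rate ratio with a 95% CI, using for all events a variance that allows for repeated events in a subject;
   - total subject-days per arm in the table header.

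   Truncate all time at death or exit.
3. Label the rates as descriptive.

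**Cost.** A few table columns, from the transfusion and event dates and times that 8.4.4 already uses plus dates of death and exit. No change to data collection is needed for the rates. The downside is that a per-day rate averages early and late risk and can dilute events caused by each transfusion, so both measures should be read together.
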